## IRB Minimal Risk Protocol Template

**Note: If this study establishes a human specimen repository (biobank) for research purposes, do not use this template. Use the Mayo Clinic Human Specimen Repository Protocol Template found on the IRB home page under Forms and Procedures at <http://intranet.mayo.edu/charlie/irb/>**

**First-time Use:** Use this template to describe your study for a new IRB submission.

1. Complete the questions that apply to your study.
2. Save an electronic copy of this protocol for future revisions.
3. When completing your IRBe application, you will be asked to upload this document to the protocol section.

**Modification:** To modify this document after your study has been approved:

1. Open your study in IRBe. Click on the study 'Documents' tab and select the most recent version of the protocol. Save it to your files.
2. Open the saved document and activate "Track Changes".
3. Revise the protocol template to reflect the modification points, save the template to your files
4. Create an IRBe Modification for the study and upload the revised protocol template.

## Research Question and Aims

Hypothesis: Patients treated with mepivacaine spinal anesthetic will have faster return of lower extremity motor function than patients treated with low-dose bupivacaine following primary total hip arthroplasty (THA) and total knee arthroplasty (TKA).

Aims, purpose, or objectives:

#1 Evaluate time to return of lower extremity motor function between mepivacaine and low-dose bupivacaine spinal anesthetic among patients undergoing primary THA and TKA. This will be assessed by measuring time from spinal anesthetic administration to postoperative achievement of Bromage 0 function (return of spontaneous ankle, knee, and hip movement) in the non-operative extremity.

#2 Evaluate postoperative outcomes potentially related to anesthetic administration including pain scores, opioid consumption, urinary retention, transient neurologic symptoms, length of PACU stay, length of hospital stay, time to participation in physical therapy and walking distance with physical therapy. This will be determined by nurse and physical therapy charting and review of the medical record.

Background (*Include relevant experience, gaps in current knowledge, preliminary data, etc.*):

Total knee arthroplasty (TKA) and total hip arthroplasty (THA) are two of the most common orthopedic procedures performed in the United States, with significant growth in procedure volume expected over the coming decades. Coupled with the growing number of surgeries, is a growing cost to perform these procedures. In order to accommodate the increased demand for total joint arthroplasty (TJA) while also reducing complications and costs, optimized recovery pathways are needed to enhance resource utilization. One way to significantly impact recovery and length of stay is for patients to participate in physical therapy earlier in their episode of care. In addition to facilitating patient readiness for discharge from the hospital, early physical therapy and ambulation reduces post-operative complications such as venous thromboembolism and pneumonia. Multiple factors related to anesthesia can affect a patient's ability to participate in physical therapy on the day of surgery; these include post-operative nausea and vomiting, orthostatic hypotension and residual muscle weakness. The use of spinal anesthesia for TJA has been shown to reduce the risk of these complications. Shortening the duration of motor blockade in spinal anesthesia can reduce the time to patient physical therapy readiness, facilitating early ambulation and discharge to home.

Historically, short to intermediate duration local anesthetics such as lidocaine have been used for spinal anesthetics in short duration knee procedures such as knee arthroscopy. However, the use of lidocaine in spinal anesthesia has been dramatically reduced due to a high incidence of transient neurologic symptoms (TNS). TNS was first defined in 1993, and is defined as a painful condition of the buttocks and thighs with possible radiation to the lower extremities, beginning as soon as a few hours after spinal anesthesia and lasting as long as ten days. All local anesthetics can cause TNS but it is most commonly associated with lidocaine and reported to occur in 4% to 40% of patients undergoing spinal anesthesia with lidocaine.

Bupivacaine has been shown to have the lowest incidence of TNS and is currently the most widely used medication for spinal anesthesia. While advantageous for avoiding TNS, bupivacaine has a slow onset time coupled a long duration of action, which can delay postoperative recovery. Low-dose bupivacaine (10 mg) regimens are increasingly used; however, issues remain with the unpredictable temporal profile. Mepivacaine (70 mg) is a shorter acting local anesthetic compared to bupivacaine with a more predictable duration of action, raising interest as an alternative for procedures such as TKA and THA with consistent performance times.

In this randomized controlled trial, mepivacaine will be compared to low dose bupivacaine spinal anesthetics. The primary outcome will be time from spinal insertion to return of motor function. Secondary outcomes will evaluate pain scores, opioid consumption, urinary retention, transient neurologic symptoms, length of PACU

stay, length of hospital stay, time to participation in physical therapy and walking distance with physical therapy.

## Study Design and Methods

**Methods:** *Describe, in detail, the research activities that will be conducted under this protocol:*

**Preoperative Visit and Anesthesiologist Assessment:** Patients meeting eligibility criteria will be approached during their surgical preoperative visit by the study coordinator in the clinic of the orthopedic Co-Principal Investigators. Those choosing to participate will be screened for inclusion and exclusion criteria. Patients will be assessed for ability to undergo a spinal anesthetic, but will be counseled that the decision between a spinal and general anesthetic will ultimately be determined by the anesthesiologist on the day of surgery. Thus, patients may be withdrawn on the day of surgery if the staff anesthesiologist does not agree with their candidacy to undergo a spinal anesthetic. Furthermore, patients will be counseled they may be withdrawn from the study if placement of a spinal anesthetic in the operating room proves unsuccessful and a general anesthetic is required.

**Randomization and Blinding:** Patients will be randomized in a 1:1 fashion. The first arm will be the "Mepivacaine" (70 mg) group and the second arm will be the "Low-Dose Bupivacaine" (10 mg) group. This trial will be conducted in a double-blinded manner. The patient and the postoperative outcomes assessors (PACU and Orthopedic Inpatient Nurses and Physical Therapists) will be the blinded parties. The anesthesia and surgical teams will not be blinded given they won't be responsible for any assessments. After a patient has been consented and enrolled, the study coordinator will randomize the patient to either Mepivacaine or Low-Dose Bupivacaine using a custom electronic randomization system which will be maintained by the study statistician. The surgical team and anesthesia team will be notified after the assignment is complete so the surgical listing can be completed with the appropriate medication.

**In Hospital Evaluation:** A standardized study card will be used to track patients throughout their various phases of care. At the time of discharge, the cards will be returned to the study coordinator for data entry in a secure spreadsheet available only to study staff. The study will begin with the anesthesiologist recording the time the spinal anesthetic is administered. The anesthesiologist will also record the time of incision, time of surgical closure, and time leaving the OR. The PACU nursing staff will then record the time of PACU entry and exit as well as the status of lower extremity function in the non-operative lower extremity at 15 minute intervals. The choices will be Bromage 3 (no movement), Bromage 2 (ankle movement only), Bromage 1 (ankle and knee movement), Bromage 0 (ankle, knee, and hip movement). Once the patient transitions to the general inpatient floor, the nursing staff will be responsible for recording motor function in a similar fashion at 15 minute intervals until the patient achieves Bromage 0 status. The physical therapy team will be responsible for recording the time of the first physical therapy session and the distance the patient ambulates during this session. Additional data points to be recorded by nursing staff will be total opioid consumption in the first 24 hours after surgery, pain scores, presence of nausea and/or vomiting, presence of orthostatic hypotension, and length of hospital stay. TNS will be evaluated twice, once during hospitalization by either the orthopedic or anesthesia team rounding on the patient on post-operative day one and a follow-up phone call performed on POD 6-9 by a study member not blinded to patient assignment. A standardized questionnaire will be used to determine the presence of symptoms of backache. TNS will be defined as new onset of back pain that radiates

bilaterally to buttock or distally. Back pain that does not meet these criteria will not be considered TNS. (ref. Anesth Analg 2005;101:661-5)

**Follow-up Evaluation:** Assessment will only take place during the hospitalization for the intended surgery. There will be a single phone call during post-operative day 6-9 for assessment of TNS.

**Resources:** *Describe the available resources to conduct the research (personnel, time, facilities, mentor commitment, etc.):*

The Co-Principal Investigator orthopedic surgeons maintain high volume practices specializing in TKA and THA. This group of surgeons works exclusively with the Co-Principal Investigator anesthesiologists who specialize in the care of TKA and THA patients.

[name] is an orthopedic surgery resident who will assist with study execution and data analysis. A study coordinator in the department of orthopedic surgery will work with the residents and the midlevel providers for the orthopedic consultants to enroll patients at the preoperative visit. Standardized study cards will be created for patients enrolled in the study so that PACU and floor nursing staff as well as physical therapists can track relevant study endpoints. These cards will be returned to the study coordinator for data entry.

[name] is a master level statistician in the Division of Biomedical Statistics and Informatics with significant experience in the department of orthopedics and executing randomized clinical trials. He will serve as the lead statistician.

All funding for the study including statistical and coordinator FTE will be covered by the Department of Orthopedic Surgery and research royalty accounts of the Co-Principal Investigators.

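### Nothing in the protocol keeps the unblinded anesthesiologist from knowing the arm before deciding, on the day of surgery, whether a patient stays in the trial as a spinal candidate

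*Combined protocol and SAP*

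**What the plan says.** The relevant text is in Study Design and Methods, and the order of events has to be put together from several paragraphs.

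- **Enrolment.** The Resources paragraph has the coordinator working with clinic staff "to enroll patients at the preoperative visit".
- **Randomisation.** Randomization and Blinding says: "After a patient has been consented and enrolled, the study coordinator will randomize the patient". No day is attached.
- **Disclosure.** The same paragraph continues: "The surgical team and anesthesia team will be notified after the assignment is complete so the surgical listing can be completed", the listing being the place where the study medication is named.
- **Blinding.** "The anesthesia and surgical teams will not be blinded given they won't be responsible for any assessments".
- **Candidacy.** Preoperative Visit and Anesthesiologist Assessment has spinal suitability assessed at the preoperative visit, but leaves the final choice between spinal and general anesthesia to the anesthesiologist on the day of surgery. At that point "patients may be withdrawn on the day of surgery if the staff anesthesiologist does not agree with their candidacy to undergo a spinal anesthetic".
- **Failed placement.** Patients are also told that "they may be withdrawn from the study if placement of a spinal anesthetic in the operating room proves unsuccessful and a general anesthetic is required".

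The Randomization section under Statistical Considerations describes online stratified dynamic allocation but not its timing. The Analysis section compares the two study groups and does not say how patients withdrawn after randomisation are handled.

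**The concern.** Read in sequence, these steps allow the person who makes the last decision on whether a patient stays in the trial to know the arm when making it. The protocol defends the lack of blinding by pointing to outcome assessment. Candidacy is not an outcome assessment, but it decides who contributes an outcome. Blinded PACU nurses, floor nurses and therapists cannot correct a selection made before they see the patient.

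There is also a conceivable reason for the arm to matter. The Background calls mepivacaine a "shorter acting local anesthetic compared to bupivacaine with a more predictable duration of action", and someone who knows the drug could weigh duration when judging a borderline case.

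Two things are at stake. If withdrawals depended on the arm, the groups compared on time to Bromage 0 would no longer be the groups that were randomised. Separately, any withdrawal after allocation can disturb the balance on procedure, gender, age and BMI that the dynamic allocation is there to keep.

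**Working it through.** **Sequence.** Enrolment is placed at the preoperative visit, randomisation after enrolment, and disclosure to the anesthesia team after randomisation in time for the listing. The candidacy decision is placed on the day of surgery. No section delays allocation or disclosure until candidacy is settled, or gives the decision to someone blinded. The In Hospital Evaluation sentence "The study will begin with the anesthesiologist recording the time the spinal anesthetic is administered" concerns data recording and does not move randomisation later. So the arm can be known at the decision. That it always is known is not stated.

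**Is this a power problem?** The plan gives a difference of 30 min, SD 65.6 min, 150 per group, two-sided α 0.05 and 80% power. Its sample size does not reproduce: n = 2(1.960 + 0.842)² × 65.6² / 30² ≈ 75.1, so 76 per group, and 150 per group gives about 97.7% power. That is a separate matter, but it means that lost numbers are not the issue here. With an assumed 10% withdrawn from each arm (135 per group), power is still about 96.4%. The question is selection.

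**Size of a selection effect (illustration).** The documents give no withdrawal rate, so the following are assumptions: a fraction p of an arm is withdrawn, being the top p of a normal predictor that has correlation ρ with time to motor recovery. The mean of those retained then shifts by

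SD × ρ × φ(z) / (1 − p), where z is the upper-p normal quantile.

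The factor φ(z)/(1 − p) is 0.1086 at p = 5%, 0.1950 at 10% and 0.2743 at 15%. The SDs come from the Sample Size section: 37 (mepivacaine pilot), 65.6 (pooled) and 89 (bupivacaine pilot).

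Withdrawal in one arm only, shift in minutes:

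| SD | ρ | p = 5% | 10% | 15% |
|---|---|---|---|---|
| 37 | 0.2 | 0.80 | 1.44 | 2.03 |
| 37 | 0.4 | 1.61 | 2.89 | 4.06 |
| 65.6 | 0.2 | 1.42 | 2.56 | 3.60 |
| 65.6 | 0.4 | 2.85 | 5.12 | 7.20 |
| 89 | 0.2 | 1.93 | 3.47 | 4.88 |
| 89 | 0.4 | 3.86 | 6.94 | 9.77 |

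Planned standard error of the difference: 65.6 × √(2/150) = 7.57 min. With the two pilot SDs it is √((37² + 89²)/150) = 7.87 min. Of the 18 one-arm cells, only 9.77 exceeds either value.

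Withdrawal in both arms on the same predictor, net shift:

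- Equal rates and equal SDs: 0.
- 5% against 15%, SD 65.6 in both: 3.60 − 1.42 ≈ 2.2 min (ρ = 0.2); 7.20 − 2.85 ≈ 4.3 min (ρ = 0.4).
- Mepivacaine 5%, bupivacaine 15%, own SDs: 4.88 − 0.80 = 4.08 min; 9.77 − 1.61 = 8.16 min.
- Mepivacaine 15%, bupivacaine 5%, own SDs: about 0.1 and 0.2 min.

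Among the unequal two-arm cases, only 8.16 exceeds the standard error. The direction depends on who is withdrawn.

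**The case against.** The strongest case against is that little room is left for the arm to act. Spinal suitability is assessed at the preoperative visit, and exclusion criterion 3 already removes patients with a contraindication to the technique. The day-of-surgery decision is therefore a second check on screened patients, and losses of 5-15% may be well above what would occur. The decision is between spinal and general anesthesia, and both arms receive a spinal. The documents describe no patient who would be a candidate with one drug and not with the other. The Background sentence on mepivacaine goes on to present its profile as suited to these operations. If withdrawals are arm-neutral, equal SDs give no net shift. Last, the sequence is partly inferred: nothing says when the listing is completed, or that the anesthesiologist judging candidacy has read the assignment.

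All of this stands and limits the size of the concern. It does not remove it. Prior screening makes late withdrawals fewer, not blind to arm, and no sentence holds the arm back until candidacy is settled.

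A reader might go further and infer that the arm is always known beforehand, that patients will be withdrawn because of it, or that the primary comparison is therefore biased. The documents support none of these. The unstated day of randomisation and the missing rule for withdrawn patients are gaps in detail. They do not show that selection takes place.

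**Conclusion.** The concern holds in a limited form. As written, the unblinded anesthesiologist can know the arm when making a decision that may remove a randomised patient, and the protocol's reason for not blinding that team does not reach this decision. Arm-dependent withdrawal is possible, not shown.

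Its size cannot be derived from the documents. In the illustration, most shifts are below the planned standard error of about 7.6 minutes. Only the extreme cases exceed it: 9.8 minutes with 15% of the bupivacaine arm alone withdrawn, and 8.2 minutes with 15% of bupivacaine against 5% of mepivacaine, both at correlation 0.4. Even 9.8 minutes is about a third of the 30-minute target. Every rate and correlation is assumed, and the pilot SDs rest on 6 and 5 patients.

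The severity is low to moderate. It is worth changing because the protection is cheap and blinded assessment cannot replace it.

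**What to change.** In Study Design and Methods (Preoperative Visit, and Randomization and Blinding), have the anesthesiologist record final spinal candidacy before the arm is released. The clinical decision and its criteria stay as they are; only the moment at which the arm becomes known changes.

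1. **Preferred:** run the existing online allocation after that record. Non-candidates are then never randomised, which also protects the allocation balance.
2. **If allocation must come earlier:** list the case without the drug name and release the arm only once candidacy is recorded. This conceals the arm but still randomises non-candidates, so it does not prevent allocation imbalance.
3. **In either case:** report any post-randomisation withdrawals, including failed placements, by arm with reasons.

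If allocation is already meant to follow the candidacy decision, one sentence saying so settles the timing.

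**Cost:** protocol wording, a change to the listing workflow (the listing now names the medication), and same-day release of the assignment with both study drugs available, for 300 patients over a few months. No new allocation system is needed. Withdrawals for failed placement would still follow disclosure of the arm; reporting makes them visible but does not remove them.

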#### Endpoints

**Primary:** Evaluate time to return of lower extremity motor function between mepivacaine and low-dose bupivacaine spinal anesthetic among patients undergoing primary THA and TKA. This will be assessed by measuring time from spinal anesthetic administration to postoperative achievement of Bromage 0 function (return of spontaneous ankle, knee, and hip movement) in the non-operative extremity.

**Secondary:** Evaluate postoperative outcomes potentially related to anesthetic administration including pain scores, opioid consumption, urinary retention, transient neurologic symptoms, length of PACU stay, length of hospital stay, time to participation in physical therapy and walking distance with physical therapy. This will be determined by nurse and physical therapy charting and review of the medical record.

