#### Analysis

[name] will lead the data analysis effort. All pre- and post-operative data will be entered by the study coordinator into standardized Excel Spreadsheets and RedCap forms as appropriate. The data will primarily be collected by the lead Study Coordinator and checked for accuracy and completeness by [name]. All outcomes will be reported descriptively using appropriate summary statistics, including 95% confidence intervals, where appropriate. Because this is a prospective, randomized trial, no formal between-group comparisons of baseline covariates will be performed. The primary study outcome will be time to return of full lower extremity motor function. Secondly, we will assess a variety of both continuous and categorical outcomes between groups including pain scores, opioid consumption, urinary retention, transient neurologic symptoms, length of PACU stay, length of hospital stay, time to participation in physical therapy and walking distance with physical therapy. Outcomes measured on a continuous scale, including time to full lower extremity motor function, length of PACU stay and hospital stay, time to participation in physical therapy, and walking distance will be compared between the 2 study groups using two-sample t-tests if the data are sufficiently normally distributed; otherwise non-parametric Wilcoxon rank sum tests will be used. Ordinal variables such as pain scores will be analyzed using non-parametric Wilcoxon rank sum tests. Binary and nominal categorical outcomes will be compared between the study groups using chi-square tests or Fisher's exact tests, if low expected cell counts are observed. All statistical tests will be two-sided and the threshold of statistical significance will be set at  $\alpha = 0.05$ .

While it is expected that the study enrollment will be complete in approximately 4 to 6 months, one interim analysis will be performed at 2 months, or once half the subjects have been enrolled, whichever comes first. The Lan-DeMets alpha spending function with O'Brien-Fleming type boundaries will be utilized to maintain the overall type 1 error rate at  $\alpha=0.05$ , regardless of the timing of the analysis.

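### Randomized patients may be withdrawn after an unsuccessful spinal by a team that knows the arm, and no analysis set or report of failures by arm guards against selective exclusion

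*Combined protocol and SAP*

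**What the plan says.** All of the following is in the Combined protocol and SAP.

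- **Withdrawal in the operating room** (Study Design and Methods, preoperative visit paragraph): patients are counselled that they may be "withdrawn from the study if placement of a spinal anesthetic in the operating room proves unsuccessful and a general anesthetic is required".
- **Earlier withdrawal** (same paragraph): "patients may be withdrawn on the day of surgery if the staff anesthesiologist does not agree with their candidacy to undergo a spinal anesthetic". This is a separate rule that acts before any attempt at a spinal.
- **Timing of randomization** (Randomization and Blinding): "After a patient has been consented and enrolled, the study coordinator will randomize the patient to either Mepivacaine or Low-Dose Bupivacaine".
- **Who knows the arm** (same paragraph): "The surgical team and anesthesia team will be notified after the assignment is complete so the surgical listing can be completed with the appropriate medication". Also: "The anesthesia and surgical teams will not be blinded given they won't be responsible for any assessments".
- **Primary outcome** (Endpoints): "measuring time from spinal anesthetic administration to postoperative achievement of Bromage 0 function".
- **TNS**: assessed on postoperative day 1 and again by telephone. Follow-up Evaluation says: "There will be a single phone call during post-operative day 6-9 for assessment of TNS".
- **Analysis**: "All outcomes will be reported descriptively using appropriate summary statistics, including 95% confidence intervals, where appropriate". The section goes on to name the tests. It does not say which randomized patients are analysed, how withdrawn patients are handled, or that failed spinals are counted by arm. Failed spinal is not among the outcomes in Endpoints.

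**The concern.** A patient withdrawn in the operating room has already been randomized. The reason given for leaving the anesthesia team unblinded is that it makes no assessments. Yet that team judges whether the spinal has succeeded and whether a general anesthetic is needed, and that judgment triggers the rule. The rule is permissive, and no one is named as making the decision.

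Two different events may fall under it. If the needle cannot be placed, no drug is given and the arm should have little to do with it. If drug is injected and the block is inadequate, the failure can depend on the drug. The protocol does not say whether the second event is covered.

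The secondary outcomes were chosen as those that the anesthetic might affect. The background section says that spinal anesthesia lowers the risk of nausea, orthostatic hypotension and residual weakness, which bear on therapy on the day of surgery. By that reasoning, patients converted to general anesthesia may differ on these outcomes, and they are the patients who can be removed. The background also says that any local anesthetic can cause TNS, so losing an exposed patient would weaken the safety comparison.

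**Working it through.** **Step 1. Order of events.** Consent and enrollment, then randomization, then notification of the surgical and anesthesia teams, then the surgical listing, then the attempt at the spinal. Withdrawal in the operating room therefore comes after randomization, with the arm known. Moving randomization to the morning of surgery would not change that.

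**Step 2. Is it repaired in the analysis?** Endpoints and Analysis contain no intention-to-treat, modified or per-protocol set, no rule for withdrawn patients, and no outcome or table for failed spinals. Nothing there restores the excluded patients.

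**Step 3. The plan's own figure, and whether power is at stake.** The only relevant figure is the sample size: SD 65.6 min, difference 30 min, 80% power, two-sided 0.05, stated as 150 per group.
- n per group = 2 × (65.6 × 2.8016 / 30)² = 75.06, rounded up to 76. The stated 150 per group is not reproduced. That is a separate matter.
- With 150 per group, SE = 65.6 × √(2/150) = 7.57 min and power is 97.7%.
- If 5% or 10% of both arms were withdrawn (assumed), 142.5 or 135 per group remain and power is 97.1% or 96.4%.

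Lost power is not the problem.

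**Step 4. Scale of a possible bias.** The documents give no failure rate, so every input here is an assumption. If a fraction f of one arm is removed and their mean would have differed by D from the rest, that arm's mean shifts by about f × D. The type I error is then 1 − Φ(1.96 − s) + Φ(−1.96 − s), with s = f × D / 7.57. With D = 60 min:

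| f (one arm only) | Shift (min) | Share of 30 min | Nominal 5% error becomes |
|---|---|---|---|
| 2% | 1.2 | 4% | 5.3% |
| 5% | 3.0 | 10% | 6.8% |
| 8% | 4.8 | 16% | 9.7% |

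Equal losses in both arms with equal D would largely cancel.

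**Step 5. What a count by arm could show.** Fisher's exact test, 150 per arm, assumed counts: 9 vs 1 gives p = 0.019, 6 vs 1 gives p = 0.12, and 4 vs 2 gives p = 0.68. Only a marked imbalance would reach significance, so the counts themselves are the useful information.

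**The case against.** The strongest case on the other side has five parts.

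- **Drug exposure.** A reader might infer that the rule removes patients who have already received study drug. The text does not say so. It speaks of placement, and its plainest meaning is that the spinal could not be placed and nothing was injected. On that reading no exposed patient is lost and any bias may be small. This stands as a limit on the point: exposure is possible, not established.
- **Loss from every outcome.** A reader might also infer that data collection stops and the telephone call is not made. That is a natural meaning of withdrawal from a study, but the handling is not stated, and secondary outcomes also come from review of the medical record. What can be said is that the protocol does not say these patients are kept.
- **Direction.** It is tempting to say that dropping failures flatters the arm with more of them. The documents do not support that. A patient with an inadequate block could reach Bromage 0 early, and dropping such patients would lengthen that arm's mean time.
- **Discretion.** It is not unlimited. A general anesthetic must also be required, and the sentence is partly consent language. That narrows the concern, but the team that judges both conditions still knows the arm.
- **Primary endpoint.** With no drug injected there is no time origin, so exclusion from that one outcome cannot be avoided. This is correct, and the remedy has to allow for it. It does not apply to pain, opioid use, urinary retention, length of stay or therapy outcomes.

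**Conclusion.** The point holds in a limited form. The plan states a rule that lets randomized patients leave the study on a judgment made with the arm known, and nothing in the analysis plan offsets it. The result may be selective exclusion from the comparisons and, if any of these patients received intrathecal drug, from TNS follow-up.

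The size and direction of any bias are unknown. The shifts of 1.2-4.8 minutes rest on assumed one-arm losses of 2-8% and an assumed 60-minute difference, and they show scale only. The documents give no ground for predicting an imbalance such as 9 vs 1, nor for saying that withdrawals would go unreported. They simply do not plan the report. The change is worth making because it is cheap, not because a large bias has been shown.

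**What to change.** These changes concern data retention and analysis. They do not touch anesthetic care.

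1. **Study Design and Methods, and the matching patient counselling.** Replace withdrawal after an unsuccessful spinal with continued data collection: the study card is completed and TNS is assessed on postoperative day 1 and days 6-9, unless the patient withdraws consent. Record whether intrathecal drug was injected.
2. **Analysis, outcomes that need no spinal time origin** (pain, opioid use, urinary retention, PACU and hospital stay, therapy outcomes). Compare by assigned arm in all randomized patients who have surgery.
3. **Analysis, primary outcome.** Compare by assigned arm in all patients who received intrathecal drug, including those converted to general anesthesia, with a spinal-only sensitivity analysis. Patients with no drug injected have no time origin. Count and report them by arm, so that a reader can check that leaving them out was balanced.
4. **TNS.** Assess in at least all patients who received intrathecal drug.
5. **Reporting.** Tabulate failed spinals and withdrawals by arm, split by drug injected or not.

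**Cost.** Wording in the protocol and counselling, plus one item on the study card. The cards, the charting and the telephone call already exist. A few general-anesthesia patients will add slight noise and dilution to the primary comparison. The spinal-only analysis shows how much, and with the stated SD the planned 150 per group leaves ample power.
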